6.5.2 SECONDARY ANALYSES

Secondary endpoints of VAS, SDC, and driving performance endpoints will be evaluated and presented similarly, however Lane Exceedance will be log transformed (more specifically $\ln(x+1)$) prior to analyses.

Tables will be presented in the same format as the primary output:

- VAS for motivation (Table 14.2.2.1)
- VAS for self-appraisal of driving performance (Table 14.2.2.2)
- Symbol Digit Coding:
 - Number of correct responses (Table 14.2.3.1)
 - Accuracy (Table 14.2.3.2)
 - Standard deviation of reaction time (Table 14.2.3.3)
- Other Driving Performance Endpoints
 - Lane exceedance; including number, maximum, and duration (Tables 14.2.4.1-14.2.4.3)
 - Average speed, speed deviation, excessive speeding count, speeding ratio (Tables 14.2.5.1-14.2.5.4)
 - Excessive Ay and Total Collisions(cornering speed threshold exceeded) (Table 14.2.6)

-
- Divided Attention (DA): Correct Responses, Omission Errors, Commission Errors, Reaction Time, Standard Deviation of Reaction Time (Tables 14.2.8.1-14.2.8.5)
 - KSS (Table 14.2.9)

A data listing for KSS will be provided (Listing 16.2.6.2). A data listing for SDC will be provided (Listing 16.2.6.3). A data listing for the two VAS results will be provided (Listing 16.2.6.4).

Additional Secondary Analyses:

Total Collisions:

Summary statistics will be provided (mean, SD, median, minimum, maximum) for total number of collisions for each time point and treatment group (Table 14.2.7). Additionally, differences in number of collisions for each pair-wise comparison will be provided with their corresponding Wilcoxon Signed Rank p-value. A bar chart will be provided pooling total number of collisions by 0, 1, 2, or ≥ 3 for all 3 treatment groups.

Self-reported readiness

Pair-wise comparisons for readiness to drive will be analyzed using McNemar's test (Table 14.2.10).

Plasma drug levels

Blood samples for the determination of plasma tolperisone concentrations will be drawn prior to each AM dosing on Days 1-3 and post-driving test (15-30 minutes after the drive) on Days 1 and 3. The relationship between initial dose effect, next day residual dose effect, and steady-state dose effect plasma drug levels and driving performance (i.e. the primary endpoint of SDLP) will be assessed by correlation. Both the Spearman and Pearson correlations will be reported (Tables 14.2.11.2-14.2.11.22).

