13.6 Pharmacodynamic Analyses

The primary endpoint, SDLP, will be analyzed using a normal theory mixed effects model with fixed effects for sequence, period, and treatment, and a random effect for subject within sequence. An unstructured covariance structure and Kenward-Roger degrees of freedom will be used.

Pair-wise comparisons (hypothesis tests) of differences in least squares means, and 95% confidence intervals on differences will be provided for:

Initial dose effect

1. cyclobenzaprine versus placebo following Day 1 PM dose
2. tolperisone versus placebo following Day 1 PM dose
3. tolperisone versus cyclobenzaprine following Day 1 PM dose

Next day residual dose effect

4. cyclobenzaprine versus placebo following Day 2 AM dose
5. tolperisone versus placebo following Day 2 AM dose

6. tolperisone versus cyclobenzaprine following Day 2 AM dose

Steady-state dose effect

7. cyclobenzaprine versus placebo following Day 3 AM dose

8. tolperisone versus placebo following Day 3 AM dose

9. tolperisone versus cyclobenzaprine following Day 3 AM dose

In addition, pair-wise within-subject differences in SDLP greater than 4.4 cm in absolute value (equal to the previously found difference between placebo and 0.05% Blood Alcohol Content (BAC) for the CRCDS) will be compared using McNemar's test. These pair-wise, within subject differences in SDLP will also be tested for symmetry about zero [6] using the maximally selected McNemar test.

Summary statistics will be provided (mean, SD, median, minimum, maximum) for SDLP for each time point and treatment group.

Additional details of analysis for secondary endpoints of VAS, SDC, KSS, and driving performance endpoints will be specified in the SAP.

The relationship between tolperisone plasma drug levels and driving performance (i.e., the primary endpoint of SDLP) will be assessed by correlational analyses.

All pharmacodynamic results will be summarized in tabular format, with summary statistics (number [n], mean, SD, median, minimum, and maximum) and change from baseline, as appropriate by time point.

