4.2 NUMBER OF SUBJECTS (STUDY POPULATION)

A sufficient number of subjects will be enrolled to ensure a total of 30 normal, healthy, male and female subjects between the ages of 21 and 55 years (at the time of informed consent) will complete all dosing periods, including the driving assessment.

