4.3 DESIGN AND TREATMENTS

This will be a randomized, placebo-controlled, multiple-dose 3-way cross-over study of the safety and cognitive effects of multiple doses of tolperisone administered TID in 30 male and female healthy volunteers. Treatment groups include 450 mg tolperisone (i.e., 150 mg administered three times daily), 30 mg cyclobenzaprine (i.e., 10 mg administered three times daily), and placebo.

Subjects will be dosed on the morning of Day 1. Approximately one hour after the second dose on Day 1, subjects will be administered the cognitive test, followed by the driving simulator examination.

On the morning of Day 2, prior to dosing, subjects will be readministered the cognitive test and driving examination to assess residual next day effects.

Subjects will repeat cognitive testing and the driving examination on the morning of Day 3, after administration of the AM study medication, to evaluate the cumulative effects of 3 days of dosing.

Subjects will be discharged on Day 3 with instructions to return to the clinic on Day 7 and Day 14 to repeat the above procedures with the second and third treatments.

A follow-up phone call will be conducted 1 week (± 3 days) following discharge from the clinic on Day 17 to assess for continued safety.

A schematic of the study design is presented in [Table 1](#).

Table 1 Schematic of Design

Hour	Day -1	Day 1	Day 2	Day 3	Days 4-7
6:00	(WASHOUT)	Breakfast	Breakfast	Breakfast	WASHOUT
7:00			Driving Simulation		
8:00		AM Dosing	AM Dosing	AM Dosing	
9:00				Driving Simulation	
10:00					
11:30		Lunch	Lunch	Lunch	
12:00					
13:00					
14:00		PM Dosing	PM Dosing	Discharge	
15:00		Driving Simulation			
16:00	Check-in				
17:00	Dinner	Dinner	Dinner		
18:00					
19:00					
20:00	Practice Cog & Driving Simulation				
21:00		HS	HS		
22:00	Bedtime	Dosing/Bedtime	Dosing/Bedtime		

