4.5 RANDOMIZATION

Prior to dosing, subjects will be randomly assigned to one of 6 treatment sequences (one for each permutation of treatment groups) and dosed with study medication (tolperisone, cyclobenzaprine or placebo) based upon a randomization scheme provided by Cognitive Research Corporation. Only the qualified person(nel) assigned to prepare and administer the study treatment will have access to the randomization schedule and dispensing records during the study period.

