8.3 FIGURES

Figure 14.2.1.1.1	Within Subject Difference Scores in SDLP by Treatment
Figure 14.2.1.2.1	Within Subject Difference Scores (Cyclobenzaprine - Placebo) (ITT Population - Day 1 PM Dose)
Figure 14.2.1.2.2	Within Subject Difference Scores (Tolperisone - Placebo) (ITT Population – Day 1 PM Dose)
Figure 14.2.1.2.3	Within Subject Difference Scores (Tolperisone - Cyclobenzaprine) (ITT Population – Day 1 PM Dose)
Figure 14.2.1.2.4	Within Subject Difference Scores (Cyclobenzaprine - Placebo) (ITT Population - Day 2 AM Dose)
Figure 14.2.1.2.5	Within Subject Difference Scores (Tolperisone - Placebo) (ITT Population – Day 2 AM Dose)
Figure 14.2.1.2.6	Within Subject Difference Scores (Tolperisone - Cyclobenzaprine) (ITT Population – Day 2 AM Dose)
Figure 14.2.1.2.7	Within Subject Difference Scores (Cyclobenzaprine - Placebo) (ITT Population - Day 3 AM Dose)
Figure 14.2.1.2.8	Within Subject Difference Scores (Tolperisone - Placebo) (ITT Population – Day 3 AM Dose)
Figure 14.2.1.2.9	Within Subject Difference Scores (Tolperisone - Cyclobenzaprine) (ITT Population – Day 3 AM Dose)
Figure 14.2.11.2.1	Within Subject Difference Scores in SDLP by Plasma Concentration for Tolperisone Day 1
Figure 14.2.11.2.2	Within Subject Difference Scores in SDLP by Plasma Concentration for Tolperisone Day 2
Figure 14.2.11.2.3	Within Subject Difference Scores in SDLP by Plasma Concentration for Tolperisone Day 3
Figure 14.2.7	Total Collisions

Neurana 115

Table 14.1.1
Study Populations

Study Population	Placebo	Tolperisone 450 mg	Cyclobenzaprine 30 mg	Overall
	(N=xx) n (%)	(N=xx) n (%)	(N=xx) n (%)	(N=xx) n (%)
Screening Failures				xx
Safety Population*	xx (xx.xx)	xx (xx.xx)	xx (xx.xx)	xx (xx.xx)
ITT Population**	xx (xx.xx)	xx (xx.xx)	xx (xx.xx)	xx (xx.xx)
PK Population ***				

* The Safety Population includes all subjects who received at least 1 dose of study drug

** The Intent-to-Treat (ITT) Population includes all randomized subjects who receive at least 1 dose of study drug in a given treatment period. This is the analysis population for efficacy analysis. Subjects will (in general) be included in all analyses for which data are non-missing.

*** The Pharmacokinetic (PK) Population includes all subjects with evaluable plasma concentration data.

SAS Program Name: Date: Source Data: Listing 16.2.2.1

Neurana 115

Table 14.1.2
Subject Disposition
(Safety Population)

Study Population	Placebo		Tolperisone 450 mg		Cyclobenzaprine 30 mg		Overall	

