Self-Reported Readiness
(ITT Population)

Day	Comparison	First Treatment	Second Treatment	N (%)	p-value*
Day 1	xxxxxxxxxxxxxxxx	No	No	xx (xxx.x%)	0.xxxx
		Yes	No	xx (xxx.x%)	0.xxxx
		No	Yes	xx (xxx.x%)	0.xxxx
		Yes	Yes	xx (xxx.x%)	0.xxxx

*McNemar's test.

SAS Program Name:

Date:

Source Data: Listing 16.2.6.X

Table 14.2.11.1
Plasma Concentration
(PK Population)

Timepoint	Tolperisone 450 mg (N=xx)	
XXXX	N	xx
	Mean (SD)	xx.xxxx (xx.xx)
	Median	xx.x
	Geometric Mean	xx.xxxx
	Min, Max	xx.xxxx , xx.xxxx

SAS Program Name:

Date:

Source Data: Listing 16.2.5.2

Table 14.2.11.2
Correlation of ln(Plasma Drug Levels) to SDLP
(ITT Population)

Day	Tolperisone 450 mg (N=xx)	
Day X	Pearson Correlation	x.xxxx
	Spearman Correlation	x.xxxx

SAS Program Name:

Date:

Source Data: Listings 16.2.5.2 and 16.2.6.1.1

Neurana 115

Table 14.3.1.1
Treatment-Emergent Adverse Events by System Organ Class, Preferred Term, and Maximum Severity
(Safety population)

Primary System Organ Class\ Preferred Term\ Severity	Placebo	Tolperisone 450 mg	Cyclobenzaprine	Overall
	(N=xx) n(%)	(N=xx) n(%)	30 mg (N=xx) n(%)	(N=xx) n(%)
Total Number of Adverse Events	xxx	xxx	xxx	xxx
Any primary system organ class	xx(xx.x)	xx(xx.x)	xx(xx.x)	xx(xx.x)
Mild	xx(xx.x)	xx(xx.x)	xx(xx.x)	xx(xx.x)
Moderate	xx(xx.x)	xx(xx.x)	xx(xx.x)	xx(xx.x)
Severe	xx(xx.x)	xx(xx.x)	xx(xx.x)	xx(xx.x)
SOC 1	xx(xx.x)	xx(xx.x)	xx(xx.x)	xx(xx.x)
Mild	xx(xx.x)	xx(xx.x)	xx(xx.x)	xx(xx.x)
Moderate	xx(xx.x)	xx(xx.x)	xx(xx.x)	xx(xx.x)
Severe	xx(xx.x)	xx(xx.x)	xx(xx.x)	xx(xx.x)
Preferred Term 1	xx(xx.x)	xx(xx.x)	xx(xx.x)	xx(xx.x)
Mild	xx(xx.x)	xx(xx.x)	xx(xx.x)	xx(xx.x)
Moderate	xx(xx.x)	xx(xx.x)	xx(xx.x)	xx(xx.x)
Severe	xx(xx.x)	xx(xx.x)	xx(xx.x)	xx(xx.x)

Etc

NOTE FOR PROGRAMMING: repeat table for treatment related (with footnote defining related) 14.3.1.2

Primary system organ classes are presented alphabetically; preferred terms are sorted within primary system organ class alphabetically. Subjects with more than one occurrence in a category are only counted once.

SAS Program Name: Date: Source Data: Listing 16.2.7.1

Table 14.3.3.1
Hematology Change From Screening
(Safety population)

Labtest (Units)		Overall (N=xx)
Screening		
Observed	n	xx
	Mean (SD)	xx.xxx (xx.xxx)
	Median	xx.xxx
	Min, Max	xx.x , xx.x
End of Study		
Observed	n	xx
	Mean (SD)	xx.xxx (xx.xxx)
	Median	xx.xxx
	Min, Max	xx.x , xx.x
End of Study Change from Screening		
	n	xx
	Mean (SD)	xx.xxx (xx.xxx)
	Median	xx.xxx
	Min, Max	xx.x , xx.x

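### The plasma-level correlations use SDLP on tolperisone without a placebo reference, while the matching figures plot within-subject differences; a same-day placebo adjustment would help at little cost

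*SAP*

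**What the plan says.** SAP 6.5.2 (Plasma drug levels) specifies that "driving performance (i.e. the primary endpoint of SDLP) will be assessed by correlation", and adds: "Both the Spearman and Pearson correlations will be reported (Tables 14.2.11.2-14.2.11.22". It names no covariate and no placebo reference. Protocol 13.6 is equally general: "The relationship between tolperisone plasma drug levels and driving performance (i.e., the primary endpoint of SDLP) will be assessed by correlational analyses".

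The mock table for 14.2.11.2, among the shells after SAP 8.3, is titled "Correlation of ln(Plasma Drug Levels) to SDLP". It has one column, tolperisone 450 mg, and prints a Pearson and a Spearman coefficient for each day.

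The figures with the corresponding numbers, listed in SAP 8.3, use another outcome. The first is "Within Subject Difference Scores in SDLP by Plasma Concentration for Tolperisone Day 1", with the same for Days 2 and 3. These titles do not say what is subtracted. The titles of Figures 14.2.1.2.1 to 14.2.1.2.9 do name both treatments.

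The trial is a "randomized, placebo-controlled, multiple-dose 3-way cross-over study" (SAP 4.3), with drives on the same three days of each period.

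**The concern.** As drafted, a programmer would correlate ln(concentration) across subjects with each subject's SDLP on tolperisone. That value contains any drug effect, the driver's usual weaving and occasion-to-occasion error. The driver component is noise for an exposure-response question, and it pulls the coefficient toward zero. If a stable trait such as body size, sex or age affects both exposure and usual weaving, the coefficient can also be biased in either direction. Each completer has a placebo SDLP from the same study day that carries information on the driver component, but the correlation tables do not use it.

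The mismatch between table and figures needs no assumption. A reader could see a pattern in the difference plot that the coefficient under the related table number does not show, or the reverse, and could not tell whether the drug or the choice of outcome is responsible. Plasma level and driving performance is a listed secondary endpoint (SAP 5.3.2), so the coefficient will be read.

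**Working it through.** The plan states no figure for this correlation, so there is none to reproduce.

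**Inputs from the documents**
- 30 completers (SAP 4.2).
- Within-subject SD of SDLP, sw, about 6 cm (SAP 6.1.1).
- Six sequences covering all treatment orders (SAP 4.5), so each completer has tolperisone and placebo drives on matching days.

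**Assumptions, not in the documents**
- Between-driver SD, sb, expressed as ICC = sb²/(sb² + sw²), at 0.3, 0.5 and 0.7.
- SDLP rises by sc = 2 or 3 cm per SD of ln concentration.
- Driver effect independent of concentration, except in the confounding check; no period effects.

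**Formulas.** Expected r = sc/√(sc² + V), where V is the noise variance:
- unadjusted SDLP: V = sb² + sw²
- tolperisone minus placebo: V = 2·sw² = 72
- adjusted for placebo SDLP: V = (sb² + sw²)(1 − ICC²)

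Example at ICC 0.7: sb² + sw² = 36/0.3 = 120, and the adjusted V is 120 × 0.51 = 61.2. With sc = 2, r = 2/√124 = 0.18 unadjusted, 2/√76 = 0.23 for the difference, and 2/√65.2 = 0.25 adjusted.

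| ICC | V unadjusted | V difference | V adjusted | r at 2 cm (unadj. / diff. / adj.) | r at 3 cm (unadj. / diff. / adj.) |
|---|---|---|---|---|---|
| 0.3 | 51.4 | 72 | 46.8 | 0.27 / 0.23 / 0.28 | 0.39 / 0.33 / 0.40 |
| 0.5 | 72 | 72 | 54 | 0.23 / 0.23 / 0.26 | 0.33 / 0.33 / 0.38 |
| 0.7 | 120 | 72 | 61.2 | 0.18 / 0.23 / 0.25 | 0.26 / 0.33 / 0.36 |

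Plain subtraction beats unadjusted SDLP only above ICC 0.5, because it removes the driver effect but doubles the error variance. The adjusted r is never below the unadjusted r.

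**Meaning of 6 cm.** If 6 cm is the SD of the paired difference, sw = 6/√2 = 4.24 cm. At 2 cm and ICC 0.5, r is then 0.32 unadjusted against 0.36 adjusted. The comparison has the same direction.

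**Cost of the degree of freedom.** Power here only gauges attenuation. By Fisher z it is Φ(atanh(r)·√(n − 3) − 1.96), with n − 4 for the partial correlation. At 3 cm it is:
- ICC 0: 70.6% unadjusted, 68.9% adjusted
- ICC 0.1: 66.3% against 65.1%
- ICC 0.2: equal
- ICC 0.5: 44% against 53%
- ICC 0.7: 29% against 48%

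At 2 cm and ICC 0.5 it is 23% against 28%.

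**Confounding check.** Assume no drug effect, ICC 0.7, and a correlation of 0.3 between ln concentration and the driver effect.
- The unadjusted correlation is 0.3 × √0.7 = 0.25.
- The partial correlation is (0.251 − 0.7 × 0.251)/√((1 − 0.49)(1 − 0.063)) = 0.11.
- With n = 30, a nominal two-sided 5% test would be falsely significant in about 27% of trials unadjusted and 9% adjusted. Adjustment reduces the bias but does not remove it.

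**The case against.** The strongest reply is that this is a secondary analysis whose shell prints coefficients without p-values, unlike the shells for SDLP, collisions and readiness to drive. The protocol synopsis also makes it conditional on the data. A reader might infer that a null correlation would be taken as proof of no exposure-response relation. The documents contain no such decision rule. This stands, and the power figures above do not describe a planned test.

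A reader might also infer that SDLP on tolperisone is known to be dominated by driver differences. The documents give no between-subject SD, and inclusion criterion 5 caps practice-drive SDLP, which trims the spread. This stands too: attenuation is possible, but its size is unknown. The 3 cm slope is favourable; at 2 cm the gain is modest, and 30 subjects remain few under either analysis.

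The SAP does not ignore the within-subject information, since the three figures use it. That is a fair point, but the figures produce no coefficient and do not name the comparator.

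Replacing SDLP by the simple difference throughout is another tempting conclusion. It fails below ICC 0.5. Putting a partial correlation in the table while leaving the figures as they are would also keep two different quantities side by side, because subtraction fixes the placebo slope at 1 and adjustment estimates it.

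Finally, the arithmetic covers Pearson correlation on SDLP, without period effects. It does not show a benefit for partial Spearman coefficients, or for sparse counts among the 21 tables from 14.2.11.2 to 14.2.11.22.

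**Conclusion.** The point holds as a minor improvement. Certain from the documents: the text and Table 14.2.11.2 give no placebo reference, the related figures use within-subject differences, and their comparator is unnamed.

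Conditional on the assumptions: adjusting for same-day placebo SDLP raises the expected r by about 0.01 at ICC 0.3, by 0.03 to 0.04 at 0.5, and by 0.07 to 0.09 at 0.7, for slopes of 2 to 3 cm per SD of ln concentration. It also limits confounding by a stable trait. If the ICC is near zero, the loss is under about 2 points of power.

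A reader might go further and suspect the main result. Nothing supports that: the non-inferiority comparison in SAP 6.5.1 does not use these correlations.

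**What to change.** - In SAP 6.5.2 and Table 14.2.11.2, state that the planned coefficients use SDLP in the tolperisone period. Beside them, report Pearson and Spearman partial correlations of ln(concentration) with tolperisone SDLP, adjusted for the same subject's placebo SDLP on the same day.
- Do the same for the other approximately continuous outcomes in Tables 14.2.11.3 to 14.2.11.22, and list which these are. Leave sparse counts such as collisions unadjusted.
- In Figures 14.2.11.2.1 to 14.2.11.2.3, name placebo as the comparator. Either plot placebo-adjusted SDLP or state that the figure shows the simple difference.

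The cost is one option in the correlation procedure, one degree of freedom, and the loss of subjects without a placebo period from the adjusted coefficient. Keeping the unadjusted coefficients lets readers see the effect of both.

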6.6 SAFETY ANALYSES

Safety analysis will be based on the safety population. Safety measures will be summarized using descriptive statistics and listed for each subject.

MedDRA thesaurus will be used to map AEs verbatim to preferred terms and body systems. WHOdrug thesaurus (Sep 1, 2016) will be used to map prior medication and concomitant medication verbatim to preferred terms and ATC Class.

6.6.1 ADVERSE EVENTS (AE)

AEs will be coded using the Medical Dictionary for Regulatory Affairs (MedDRA version 20.0) coding system. Frequency tables will be presented by dose group summarizing:

- all treatment emergent AEs (Table 14.3.1.1),
- all treatment emergent treatment-related (defined as possibly or definitely related) AEs (Table 14.3.1.2),
- all serious treatment emergent AEs (Table 14.3.2.1)
- all AEs leading to discontinuation (Table 14.3.2.2).

Listings will be presented to provide:

- all AEs (Listing 16.2.7.1)
- all treatment related AEs (terms including definitely and probably related) (Listing 16.2.7.2).

6.6.2 CLINICAL LABORATORY EVALUATIONS

Each laboratory examination observed value and change from baseline (when appropriate) will be summarized for hematology, blood chemistry, and urinalysis for each treatment at screening and end of study (Tables 14.3.2.1, 14.3.3.1, and 14.3.4.1). Shift tables will be constructed for hematology, blood chemistry, and urinalysis (Tables 14.3.2.2, 14.3.3.2, and 14.3.4.2).

Subject laboratory examination data listings will be provided (Listings 16.2.8.1-16.2.8.4). All clinical laboratory values outside normal range (including Screening/Visit 1 and EOS/Day 17 examination) will be listed by treatment and subject number, including demographic information and flagging of values (Listing 16.2.8.5).

6.6.3 PHYSICAL EXAMINATION

A listing of physical examination data will be provided by subject (Listing 16.2.8.7.1). Subjects with any changes in the physical examination evaluation from Screening/Visit 1 to EOS/Day 17 will be listed (Listing 16.2.8.7.2).

6.6.4 VITAL SIGNS

Summary statistics (n, mean, standard deviation, minimum, median, and maximum) will be presented for the raw values and change from baseline (defined as pre-dose Day 1 Period 1) values at each time point for all vital signs (including orthostatic vital signs) (Tables 14.3.6.1-14.3.6.5.3).

A data listing of vital sign data will be provided by treatment and subject (Listing 16.2.8.9).

6.6.5 12-LEAD ELECTROCARDIOGRAM

Each ECG parameter observed value and change from screening will be summarized (Table 14.3.7.1). The ECG results will be categorized as normal, clinically significant abnormal, and not clinically significant abnormal. A shift table for ECG abnormalities will be provided (Table 14.3.7.2).

A data listing of ECG results for each parameter will be provided by subject (Listing 16.2.8.8.1). A data listing of ECG normality will be provided by subject (Listing 16.2.8.8.2).

6.7 CONCOMITANT MEDICATIONS

Concomitant medications will be summarized (n and %) by ATC class and preferred term (Table 14.3.8.2).

Concomitant medications will be listed by subject (Listing 16.2.8.6.2).

6.8 CONCENTRATION DATA

Concentration data will be summarized (n and %) by treatment (Table 14.2.11).

Concentration data will be listed by treatment and subject (Listing 16.2.5.2).

6.9 ADDITIONAL COLLECTED DATA

General comments will be listed by subject (Listing 16.2.8.10).

8 TABLES, LISTINGS, AND FIGURES

Tables, listings, and figures numbering and titles will be finalized by the Sponsor at a later date.

